There are no study related costs to the participant outside of what would be recommended for standard care. Whether enrolled in the chlorhexidine gluconate or povidone iodine, participants will not be billed outside of standard operating procedure for their surgical care.

23. Compensation

There will be no monetary compensation for involvement in the study.

24. Compensation for Research-Related Injury

If participants are injured or become sick as a result of this study, UNMHSC will provide emergency treatment at the study participant's cost. No commitment is made by the University of New Mexico Health Sciences Center to provide free medical care or money for injuries to

participants of the study. Reimbursement for treatment for all related costs of care will be sought from the participant insurer, managed care plan, or other benefits program. The participant will be responsible for any associated co-payments or deductibles required by the insurance. Participants will be encouraged to report any illness or injury they believe to be related to the study to the investigator or research staff. Participants will be given telephone contact information for the urogynecology office for the purpose of asking any questions or stating any concerns about the study or treatment as a research subject. They may also be directed toward the HRPO. This language will be stated in the written consent document, and reviewed during the informed consent process

25. Consent Process

Patients will be approached about the research study at the urogynecology clinic at UNM Eubank and at SRMC or the associated hospitals at UNM Hospital or SRMC Hospital during a discussion for the management of their urogynecologic condition. Each patient undergoes counseling in a private room with a closed door to ensure privacy. The physicians in the urogynecology division and research staff will be able to obtain consent after the participants have been counseled about their condition. Our division routinely treats this condition and are highly qualified to counsel patient regarding the risks, benefits, alternatives for the treatment. Those recruited will have already decided to undergo surgical management for their urogynecologic conditions. Hence, they will not be coerced into performance of any “extra” treatments. Additionally, care will not be withheld if they decide not to participate.

The patients who would like to participate in the study will be consented during their new or return visit in the urogynecology clinic or by phone due to the current pandemic. Verbal consent will be noted on the updated consent form with a space to also sign. Due to the pandemic, research coordinators are mainly working from home and going through the consent with participants by phone for the safety of everyone. Privacy is still maintained as the coordinator ensures they have a place they can talk privately by phone. They will have these multiple opportunities to ask any questions that they may have, and they will also be provided with the clinic’s contact information to get in touch with research investigators to address any additional questions or concerns. If they decide to participate at the next visit, they will be allowed to join as long as their surgical procedure has not been completed.

Subjects will be reassured that participation is completely voluntary and does not affect their treatment, their relationship with their providers, or the university to minimize the possibility of coercion or undue influence. The patients will be asked that they understand the opportunity to participate and their complete freedom to decline. This will also be asked if they understand and if they have any questions. There is no minimum time period needed between informing

the patient of the study and time of consent. Subjects will be encouraged to take as much time as they need.

This study will obtain HIPAA authorization prior to enrollment. HIPAA authorization is imbedded within the study consent form, which will be reviewed with all participants by the physician or research staff obtaining consent. Specific information that will be obtained includes prior medical history, surgical history, reproductive health history including child bearing, drug allergies, age, and ethnicity. This information will be obtained by health care providers, not research coordinators, as deemed necessary for a more complete and accurate medical history of the patient.

The HIPAA form is included in the consent attached.

Subjects not fluent in English

Spanish speaking patients will be included in the study, and fully translated consents will be available in Spanish. Consent process for Spanish speaking patients will be conducted through a Spanish interpreter or with a research protocol member fluent in Spanish.

Cognitively Impaired Adults/Adults Unable to Consent/Use of a Legally Authorized Representative

NA. Cognitively impaired subjects will not be included in this study.

Subjects who are not yet adults (infants, children, teenagers)

NA. Only subjects ≥ 18 years of age will be included in this study.

Waiver or Alteration of Consent Process (consent will not be obtained, required element of consent will not be included, or one or more required elements of consent will be altered)

NA. There will be no waiver or alteration of the consent process.

26. Documentation of Consent

We plan to document consent, and the Consent form is attached. We do not plan on collecting/storing tissue samples.

27. Study Test Results/Incidental Findings

We do not intend to share study test or procedure results with study participants. Additionally, we do not anticipate that the research being conducted will result in incidental findings. Every patient will receive the practice's standard of care regarding workup and treatment of urogynecologic conditions, which may include different laboratory tests, urine culture or

urodynamic testing if unclear cause of incontinence, prolapse, or other urogynecologic condition, or imaging studies, as determined by their other active medical issues. These results are not directly a part of the research being conducted and will hence be disclosed to the patient. They will not, however, affect randomization.

28. Sharing Study Progress or Results with Subjects

We do not intend to share study progress with participants while the study is underway as not to introduce bias. We do not intend to seek out study participants to disseminate information once the study is complete. Women who are interested in the results will be provided the information where to read the manuscript once it is published. Study results for individual participants will not be shared.

29. Inclusion of Vulnerable Populations

There will not be any vulnerable populations included in this study. Those electing for treatment of urogynecologic conditions will not be coerced into doing so, nor will they be coerced into participating in this trial.

30. Community-Based Participatory Research

N/A. There will be no involvement of the community in this research.

31. Research Involving American Indian/Native Populations

NA. This research does not specifically target this population. If an American Indian woman is a candidate for this study she will be offered participation

32. Transnational Research

NA. This study is not transnational.

33. Drugs or Devices

Surgical preparations including chlorhexidine gluconate 4% solution as well as povidone iodine will be used for surgical preparation. According the American College of Obstetricians and Gynecologists (ACOG):

“Vaginal cleansing with either 4% chlorhexidine gluconate or povidone-iodine should be performed before hysterectomy or vaginal surgery. Currently, only povidone-iodine preparations are approved by the U.S. Food and Drug Administration (FDA) for vaginal surgical site antisepsis. The CDC (Berrios-Torres SI) recommended alcohol-based preparations, which typically include

chlorhexidine, for external perioperative skin preparation, based on studies that suggest superiority over aqueous povidone-iodine preparations, raising the question of chlorhexidine use for vaginal surgical site antisepsis. In the United States, 4% chlorhexidine gluconate soap (containing 4% isopropyl alcohol) is often used off-label to prepare the vagina in women with iodine allergy, and some U.S. institutions prefer it for routine cases. To avoid irritation, chlorhexidine gluconate with high concentrations of alcohol (eg, 70% isopropyl alcohol, commonly used for skin preparation) is contraindicated for surgical preparation of the vagina. However, solutions that contain lower concentrations, such as the commonly used 4% chlorhexidine gluconate soap containing 4% alcohol, are usually well tolerated and may be used for vaginal surgical preparation as an alternative to iodine-based preparations in cases of allergy or when preferred by the surgeon.”

Additionally chlorhexidine gluconate has been shown to be safe and effective as a vaginal presurgical preparation in a pre-post study. ([Al-Niaimi A](#)). The 53 patients receiving chlorhexidine gluconate in that trial actually experienced less vaginal irritation than those receiving povidone iodine, and did not have any serious adverse events.

34. Principal Investigator’s Assurance

By submitting this study in the Click IRB system, the principal investigator of this study confirms that:

- The information supplied in this form and attachments are complete and correct.
- The PI has read the Investigator’s Manual and will conduct this research in accordance with these requirements.
- Data will be collected, maintained and archived or destroyed per HSC Data Security Best Practices, including:
 1. **Best Practice for data collection** is for it to be directly entered onto a data collection form that is in a secured access folder on an HS drive behind a firewall, or in a secure UNM Data Security approved system such as RedCap.
 2. **Data collection of de-identified data**, if done in a clinical setting or other setting that does not allow direct entry into a secured system, may be done temporarily using a personal or university owned electronic storage device or hard copy document. **The important security safeguard is that no identifiers be include if the data is entered or stored using an untrusted device or storage.**
 3. **Permanent (during data analysis, after study closure)** storage must reside on HSC central IT managed storage. Processing of data (aggregation, etc.) are to be carried out in such a way as to avoid creating/retaining files on untrusted storage devices/computers. Trusted devices are HSC managed and provide one or more of following safeguards: access logs, encryption keys, backups, business continuity and disaster recovery capabilities.

4. **Alternate storage media** must be approved by HSC IT Security as meeting or exceeding HSC central IT provided security safeguards.

Checklist Section

This section contains checklists to provide information on a variety of topics that require special determinations by the IRB. Please complete all checklists relevant to your research.

I. Waivers or Alterations of Consent, Assent, and HIPAA Authorization

NA. We are not requesting alterations of consent, assent, nor HIPAA Authorization

A. Partial Waiver of Consent for Screening/Recruitment

NA. We are not requesting a partial waiver of consent for screening/recruitment.

B. Partial Waiver of HIPAA Authorization for Screening/Recruitment

We are requesting a partial waiver of HIPAA authorization for screening/recruitment.

We will review medical records of participants who have any missing questionnaire data, such as medical history, physical examination and demographic data. Consent will be obtained from patients to review this information.

C. Waiver of Documentation of Consent

NA. We are not requesting a waiver of documentation of consent

D. Alteration of Consent

NA. We are not requesting an alteration of consent.

E. Full Waiver of Consent/Parental Permission

NA. We are not requesting a full waiver of consent/parental permission.

F. Full Waiver of Consent/Parental Permission (Public Benefit or Service Programs)

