20. Recruitment Methods	18
21. Provisions to Protect the Privacy Interests of Subjects	19
22. Economic Burden to Subjects	19
23. Compensation	19
24. Compensation for Research-Related Injury	19
25. Consent Process	20
26. Documentation of Consent	21
27. Study Test Results/Incidental Findings	21
28. Sharing Study Progress or Results with Subjects	22
29. Inclusion of Vulnerable Populations	22
30. Community-Based Participatory Research	22
31. Research Involving American Indian/Native Populations	22
32. Transnational Research	22
33. Drugs or Devices	22
34. Principal Investigator's Assurance	23

1. Objectives

The primary objective of this research study is to perform a single-blinded, non-inferiority randomized-controlled trial to compare the effectiveness of two pre-surgical vaginal antiseptic cleaning solutions prior to pelvic surgery (which may include a vaginal approach or surgery on the vagina). Our central hypothesis is that chlorhexidine gluconate will be non-inferior to povidone iodine and that both antiseptic solutions will equally prevent postoperative infections. The specific aims are:

Aim 1: To compare postoperative urinary tract infection (UTI) rates between women cleaned with chlorhexidine gluconate (CHG) versus povidone iodine (PI) preoperatively. For the purposes of this study, UTI will be defined as: 1) greater than 100,000 CFUs on culture, or 2) at least 10,000 colony forming units on urine culture, in a symptomatic patient, or 3) patient reported UTI symptoms empirically treated within 2 weeks after surgery. Our primary **hypothesis** is that chlorhexidine gluconate will be non-inferior to povidone iodine with respect to the number of UTIs identified and treated within 2 weeks of surgery.

Aim 2: To compare postoperative culture proven urinary tract infection (UTI) rates between women cleaned with chlorhexidine gluconate (CHG) versus povidone iodine (PI) preoperatively. For the purposes of this aim UTI will be defined as: 1) greater than 100,000 CFUs on culture, or 2) at least 10,000 colony forming units on urine culture, in a symptomatic patient. Our primary **hypothesis** is that chlorhexidine gluconate will be non-inferior to povidone iodine with respect to the number of UTIs identified and treated within 2 weeks of surgery.

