Aim 3: To compare postoperative rates of surgical site infection (SSI) in women who receive chlorhexidine gluconate versus povidone iodine vaginal antiseptic preparation preoperatively, defined as per CDC guidelines (described below). **Hypothesis:** Chlorhexidine gluconate will demonstrate a non-inferior rate of postoperative SSI compared to povidone iodine.

Aim 4: evaluate vaginal and vulvar irritation for post groups on postop day 1 as measured by a 5-point vaginal irritation scale previously used in a safety and tolerability study examining vaginal chlorhexidine gluconate (Al Niaimi et al) **Hypothesis:** Chlorhexidine gluconate will demonstrate a non-inferior rate of postoperative vaginal and vulvar irritation for postop day 1.

2. Background

Steady improvements have been made in surgical infection control over the past century including improved instrument sterilization methods, operating room ventilation, surgical barriers including gowns and drapes, surgical technique, preoperative antimicrobial prophylaxis, and preoperative cleaning or prepping of the surgical site. Despite these advancements, UTIs and SSIs continue to be a common cause of postoperative morbidity.

Urinary Tract Infections are one of the most common post-operative complications associated with urogynecologic surgery. One study estimated that 33% of women develop UTIs in the 12 week period following surgical treatment for stress urinary incontinence (Anger et al). UTIs are associated with increased health care costs, antibiotic resistance, and morbidity and mortality for patients. Because UTIs are so common, they are used as a quality metric and tracked by the Joint Commission, the Centers for Medicare and Medicaid Services (CMS), and National Surgical Quality Improvement Program (NSQIP), among others.

Another concern following pelvic surgery (which may include a vaginal approach or surgery on the vagina) is development of surgical site infections (SSI). A recent study found that SSIs were among the most common healthcare-associated infection, accounting for 31% of all healthcare-associated infections (HAI) among hospitalized patients. (Magill 1) Vaginal surgery is classified as clean-contaminated procedures because of the natural bacterial flora of the vagina. This generally increases infection risk over clean procedures.

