Several studies demonstrate decreased SSI rates when chlorhexidine gluconate is used for abdominal preoperative antisepsis. Common abdominal surgeries such as hysterectomy and cesarean section demonstrate 44% and 19% lower odds when chlorhexidine gluconate is used instead of povidone iodine for preoperative surgical site antiseptic preparation. (Uppal et al) (Elshamy et al).

CHG is also known to have a longer duration of action than PI. While iodine has a duration of action of 2 hours, CHG has been characterized as having a duration of action of 6 to 48 hours depending on the level of alcohol concentration in the antiseptic solution. (Hemani et al)

Because of this, chlorhexidine is the preferred antiseptic of choice prior to abdominal surgeries.

For vaginal surgery, povidone iodine is the only FDA approved antiseptic agent. Because of this, some institutions limit or restrict the use of chlorhexidine vaginally. However, chlorhexidine has been shown to be a safe and effective vaginal presurgical antiseptic. (Al-Niaimi) The American College of Obstetricians and Gynecologists (ACOG) recommend that either CHG or PI are acceptable antiseptic agents. We are not aware of any studies directly comparing perioperative infection rates between CHG and PI at the time of pelvic surgery (which may include a vaginal approach or surgery on the vagina). A recent systematic review evaluating preoperative antisepsis at the time of vaginal hysterectomy identified minimal data, although one study which used bacterial colonies as a surrogate of SSI showed fewer bacteria sampled serially during a vaginal hysterectomy with CHG versus PI (Culligan). This corroborates the notion that CHG has a longer residual effect at the site of application over PI.

There have been no studies to specifically determine non-inferiority of chlorhexidine gluconate to povidone iodine for preoperative vaginal preparation prior to urogynecologic procedures with regard to either urinary tract infection or surgical site infection rates. Therefore, the primary objective of this study is to perform a single-blinded, non-inferiority randomized controlled trial to compare the effectiveness of two pre-surgical vaginal antiseptic cleaning solutions prior to pelvic surgery.

3. Study Design

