The primary outcome of this study is to determine rates of urinary tract infections in the period 2 weeks post-surgery for both cohorts. For the purposes of this study, UTI has been defined in section 1 (objectives), aim 1. We have powered the study based on a 10% difference in UTI rates between groups within 2 weeks of surgery. Based on a non-inferiority study design and a between group difference of less than or equal to 10%, we need 58 patients per group (chlorhexidine gluconate versus povidone iodine) to detect no difference with an alpha =0.05 and with 80% power. Assuming a high dropout rate of 20%, we will enroll a total of up to 200 patients (100/group), or until we reach our primary endpoint of 2 week follow up for 116 patients, or 58 patients in each group. We have increased the numbers due to COVID-19 and loss to follow-up.

This is not a multi-center study. Data will be housed at the Eubank clinic.

6. Study Timelines

Timeline	May 2019- April 2020	May 2020-Sept 2020
Subject recruitment, therapy, through 3 month follow up	x	x
Data analysis		x
Manuscript preparation		x

Over the past 12 months, 318 urogynecology cases were performed at UNM and SRMC. Assuming a conservative estimate of 50% enrollment, recruitment of up to 200 patients would be feasible over the next 3 month period.. Since subjects will be followed for 6 weeks after surgery, it may take up to 14 months to collect 6 weeks of follow up data. We estimate that data analysis, manuscript preparation and publication will take an additional 10 months.

7. Study Endpoints

The **primary endpoint** of our study is to determine the incidence of urinary tract infections within weeks of surgery in women who undergo pelvic surgery (which may include a vaginal approach or surgery on the vagina) with either chlorhexidine gluconate or povidone iodine vaginal antiseptic preparation. Our **secondary endpoints** are to investigate SSI rates in the two groups at 6 weeks, and vaginal irritation on the first postoperative day.

Given the extremely low-risk nature of the therapeutic interventions, we do not have any **safety endpoints**. However, any patients noted to have an allergic response will be treated according to the normal standard of care depending on the severity of their allergic reaction.

8. Research Setting

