 - c. an abscess or other evidence of infection involving the organ/space that is detected on gross anatomical or histopathologic exam, or imaging test evidence suggestive of infection. AND meets at least one criterion for a specific organ/space infection site.

13. Data Analysis

Data Analysis: Between and within group differences will be evaluated using Wilcoxon-Mann-Whitney test for categorical variables and t-tests for continuous variables. If there are any baseline differences between groups, a multivariate analysis will determine the contribution of these differences to observed differences (if any) between groups.

Power Analysis: Power analysis was performed based on previously reported rates of postoperative urinary tract infection after urogynecologic surgery as well as rates of relative reduction in infection with chlorhexidine presurgical preparations as opposed to povidone iodine. To achieve significance for a non-inferiority study using these assumptions we would need 116 patients, 58 per group to detect this difference with $\alpha = 0.05$ and with 80% power.

To allow for a dropout or loss to follow up of 20% due to the pandemic, we will enroll at least 200 patients.

Comparative Cost Analysis

The cost analysis will be conducted from patient and health system perspective and will be expressed as incremental cost required to prevent one episode of UTI.

Direct and indirect cost of health care utilization will be obtained when episodes of UTI occur, including the patient reported travel expenses and copays to obtain care, cost of UTI diagnosis with urine dipstick, urinalysis, and urine culture standardized to University of New Mexico Health Sciences Center institutional pricing as well as the cost of antibiotics for treatment.

14. Provisions to Monitor the Data to Ensure the Safety of Subjects

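### Every aim stops at non-inferiority and the only planned UTI test is an unlinked test of difference, so neither non-inferiority nor a chlorhexidine advantage has a pre-specified decision rule

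*Combined protocol and SAP*

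**What the plan says.** **Hypotheses (Section 1).** The central hypothesis is non-inferiority and also that "both antiseptic solutions will equally prevent postoperative infections". Aim 1, the primary aim, states: "chlorhexidine gluconate will be non-inferior to povidone iodine with respect to the number of UTIs identified and treated within 2 weeks of surgery". The second aim (culture-proven UTI) repeats that sentence and also calls it a primary hypothesis. Aim 3 reads "Chlorhexidine gluconate will demonstrate a non-inferior rate of postoperative SSI compared to povidone iodine", and Aim 4 reads "Chlorhexidine gluconate will demonstrate a non-inferior rate of postoperative vaginal and vulvar irritation for postop day 1". No superiority hypothesis and no rule for moving from non-inferiority to superiority appears anywhere.

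**Background (Section 2).** Abdominal hysterectomy and cesarean section are said to "demonstrate 44% and 19% lower odds when chlorhexidine gluconate is used instead of povidone iodine" for skin preparation. These are SSI results.

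**Sample size.** Section 5 begins "Based on a non-inferiority study design and a between group difference of less than or equal to 10" per cent and asks for 58 per group "to detect no difference with an alpha =0.05 and with 80% power". Section 13 gives the basis as earlier UTI rates together with "rates of relative reduction in infection with chlorhexidine presurgical preparations as opposed to povidone iodine". Neither section states the rates used, the size of the reduction, or whether alpha is one- or two-sided.

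**Analysis (Section 13).** Group differences are to be assessed with a Wilcoxon-Mann-Whitney test for categorical variables and t-tests for continuous ones. No confidence interval and no comparison with a margin is described.

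**The concern.** The hypotheses and the analysis do not meet. The hypotheses are about a margin; the planned test is about zero difference. A non-significant difference test does not show that chlorhexidine is within 10 points of povidone iodine, and the central hypothesis of equal prevention invites exactly that misreading.

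In the other direction, Section 13 indicates that the trial was sized on an expected benefit of chlorhexidine, but the plan does not say how benefit would be concluded. If the difference test came out significant in favour of chlorhexidine, nothing says whether that counts as a trial conclusion, whether it depends on non-inferiority being met first, or at what level it is judged. The wording would be settled after the data are seen.

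**Working it through.** **1. The plan's own figure.** For non-inferiority on a risk difference with margin M, the number per group is n = (z_alpha + z_power)^2 x [pC(1-pC) + pP(1-pP)] / (M + pP - pC)^2, where C is chlorhexidine and P is povidone iodine. Take M = 0.10, reading the 10% as percentage points, and 80% power. At one-sided 0.05, (1.645 + 0.842)^2 = 6.183.

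- 30% P vs 20% C: 6.183 x (0.21 + 0.16) / 0.20^2 = 57.2, so 58.
- Equal rates of 20%: 6.183 x 0.32 / 0.10^2 = 197.8, so 198.
- Equal rates of 33%: 274.
- Equal rates of about 4.9%: 58.

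At one-sided 0.025, 20% vs 11.2% (a risk ratio of 0.56) also gives 58. The 58 therefore cannot be traced to one set of inputs. At povidone iodine rates of 20-33% it works only if chlorhexidine is assumed better, which agrees with Section 13. At equal rates near 5% it needs no such assumption.

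**2. A difference test does not answer Aim 1.** Take 58 per arm and an observed 20% in both arms, so the difference is exactly zero and the test is as non-significant as it can be. The standard error is sqrt(2 x 0.20 x 0.80 / 58) = 0.0743. The upper limit at one-sided 0.05 is 1.645 x 0.0743 = 12.2 points, and at one-sided 0.025 it is 1.96 x 0.0743 = 14.6 points. Both exceed 10, so non-inferiority is not shown.

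**3. Cost in alpha of a second step.** Let d = pC - pP, with Newcombe upper limit d + sqrt[(uC - pC)^2 + (pP - lP)^2], where l and u are Wilson limits. An upper limit below zero is always below 10 points, so superiority can never be declared without non-inferiority. Exact binomial enumeration under equal rates gives these false-superiority rates:

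- 58 per arm, rates 5-30%: 1.3-2.6% (nominal 2.5%).
- 80 per arm, rates 3-30%: 2.9-5.1% (nominal 5%).

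No alpha split is needed for this one endpoint.

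**4. What the second step could yield.** Assumptions: the Section 2 odds ratios of 0.56 and 0.81 are borrowed for UTI, and the povidone iodine rate is 10%, 20% or 33%. The documents give no 2-week rate; 33% is their 12-week figure after stress incontinence surgery. An odds ratio of 0.56 turns 10% into 5.9% (odds 0.1111 x 0.56 = 0.0622; 0.0622/1.0622), 20% into 12.3% and 33% into 21.6%. Arm sizes are 58 (Section 5's stopping point) and 80 (100 per group less 20%). The table gives the chance that the Newcombe upper limit is below zero:

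| Odds ratio | n per arm | one-sided 0.05 (10/20/33%) | one-sided 0.025 (10/20/33%) |
|---|---|---|---|
| 0.56 | 58 | 19.3 / 30.1 / 39.7% | 10.0 / 19.1 / 28.2% |
| 0.56 | 80 | 25.3 / 37.6 / 49.2% | 15.0 / 25.8 / 36.2% |
| 0.81 | 58 | 8.9 / 11.2 / 12.9% | 4.1 / 6.1 / 7.6% |
| 0.81 | 80 | 10.5 / 13.0 / 15.5% | 5.5 / 7.3 / 8.9% |

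For comparison, an ordinary two-sided 0.05 test of 30% vs 20% has 23.5% power at 58 per group and would need 294 per group for 80%. The second step will usually fail even when chlorhexidine is better.

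**The case against.** The strongest reply is that this is a choice, not an error. Section 2 explains why non-inferiority is the question: povidone iodine is the only FDA-approved vaginal agent, some institutions restrict chlorhexidine, and no trial has tested non-inferiority. Leaving out a superiority claim biases nothing. That stands, and it is why the superiority step is offered as an improvement. It does not cover the other half of the point: the analysis section has no method for the non-inferiority question the trial does ask.

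Four stronger readings are tempting, and the documents do not support them.

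- A reader might infer that no planned analysis could show fewer UTIs with chlorhexidine. Section 13 does plan a between-group test; what is missing is its link to a hypothesis, an order and a decision rule.
- A reader might infer that the background assumes a lower UTI rate with chlorhexidine. The 44% and 19% figures are SSI odds with abdominal antisepsis, the vaginal hysterectomy study cited measured bacterial counts, and the central hypothesis is equality. Only the unquantified sentence in Section 13 points to an assumed benefit.
- A reader might infer that one added sentence on superiority would do. The plan names no interval, level or sidedness, so these must be written first.
- A reader might infer that a result within the margin yet significantly worse for chlorhexidine is a material risk. At 6% vs 3% with 80 per arm, the Newcombe interval puts its chance at 0.0% at one-sided 0.05. A Wald interval makes it look commoner because it behaves poorly at such low counts. A reporting rule for this case is only a safeguard.

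**Conclusion.** The point holds in this form. All four hypotheses are non-inferiority only, and the one planned comparison cannot establish non-inferiority and gives a finding in favour of chlorhexidine no defined standing. A fixed sequence on one interval settles both.

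The superiority step is a low-cost improvement of limited yield: about 10-49% with an odds ratio of 0.56 and about 4-16% with 0.81, across the arm sizes, levels and rates in the table. Those figures rest on borrowing SSI odds ratios for UTI and on assumed 2-week rates, so they illustrate and do not predict. That the step costs no alpha is true within Aim 1 only: Aim 2 is also labelled a primary hypothesis, and no multiplicity rule covers the four aims.

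**What to change.** In Section 1 (Aim 1) and Section 13:

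1. Define one confidence interval for the 2-week UTI risk difference, chlorhexidine minus povidone iodine. State its level and sidedness, and use a method suited to low counts, such as Newcombe.
2. Step 1: conclude non-inferiority if the upper limit is below 10 percentage points.
3. Step 2, only if step 1 is met: conclude superiority if the same upper limit is below zero, with no alpha adjustment for this endpoint.
4. State that a failed step 2 is not evidence of equality.
5. State that an interval within the margin but wholly above zero is reported as a higher UTI rate with chlorhexidine.
6. State that the Section 13 difference test on UTI is read only through this sequence.
7. State that the sequence covers Aim 1 only, and how Aim 2 ranks against it.

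The cost is a short paragraph, written before outcomes are seen by arm. Step 2 needs no extra patients, data or alpha within Aim 1. Fixing the level may, however, show whether 58 is enough for step 1: with 30% vs 20%, the formula above gives 58 per group at one-sided 0.05 but 73 at one-sided 0.025.
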